4 STUDY DRUG

Study drug includes both Investigational [Medicinal] Product (IP/IMP) and Non-investigational [Medicinal] Product (Non-IP/Non-IMP) and can consist of the following:

- All products, active or placebo, being tested or used as a comparator in a clinical trial.
- Study required premedication, and
- Other drugs administered as part of the study that are critical to claims of efficacy (eg, background therapy, rescue medications)

BMS-986158 will be administered orally. The appropriate number of capsules, based on the assigned dose level, will be administered.

Doses should be taken at approximately the same time each day. Dose can be taken with or without food (defined as no food approximately 1 hour prior and 2 hours after dose) and this information should be recorded in the study diary and the CRF. If a dose is missed on a dosing day, the dose should be skipped and dosing should be resumed at the next scheduled dose. Subjects may be dosed on the regularly scheduled day in the following week. Doses of BMS-986158 should not be repeated if the subject vomits more than 2 hours after taking the dose. Missed dosing information should be recorded in the study diary, the CRF, and medical record along with a description of the reason for the missed dose. The next dosing day should be kept on schedule. If the subject misses a dose, BMS must be notified. Subjects should bring all drug containers to each study visit for drug reconciliation. Empty drug containers should be collected at each visit (or reconciled at least once a month, whichever is prior). Table 4-1 indicates the dose and dosage form to be administered in this study.

Product Description Class and Dosage Form	Potency	Primary Packaging (Volume)/ Label Type	Secondary Packaging / Label Type	Appearance	Storage Conditions (per label)
BMS-986158-01	0.25 mg	Bottle/Open Label	N/A	Capsule	Refer to label on the container
BMS-986158-01	2.0 mg	Bottle/Open Label	N/A	Capsule	Refer to label on the container
Nivolumab (BMS-936558) solution for injection	100 mg/vial (10 mg/mL)	Vial/Open Label	Box	Vial	Refer to label on the container

The time of dose administration will be called "0" hour.

Product description and storage information is described in Table 4-1.

For study drugs not provided by BMS and obtained commercially by the site, storage should in accordance with the product label.

The product storage manager should ensure that the study treatments are stored in accordance with the environmental conditions (temperature, light, and humidity) as determined by BMS. If concerns regarding the quality or appearance of the study treatments arise, the study treatments should not be dispensed and BMS should be contacted immediately.

IP documentation must be maintained that includes all processes required to ensure drug is accurately administered. This includes documentation of drug storage, administration and, as

applicable, storage temperatures, reconstitution, and use of required processes (eg, required diluents, administration sets).

Infusion-related supplies (eg, IV bags, in-line filters, 0.9% NaCl solution) will not be supplied by the Sponsor and should be purchased locally if permitted by local regulations.

Please refer to the current version of the IB and/or pharmacy reference sheets for complete storage, handling, dispensing, and infusion information for nivolumab.

4.1 Investigational Product

An IP, also known as investigational medicinal product in some regions, is defined as a pharmaceutical form of an active substance or placebo being tested or used as a reference in a clinical study, including products already with a marketing authorization but used or assembled (formulated or packaged) differently than the authorized form, or used for an unauthorized indication, or when used to gain further information about the authorized form.

The IP should be stored in a secure area according to local regulations. It is the responsibility of the investigator to ensure that IP is only dispensed to study subjects. The IP must be dispensed only from official study sites by authorized personnel according to local regulations.

In this protocol the IP are BMS-986158 and nivolumab. BMS-986158 in combination with nivolumab will only be pursued on review of safety information and the totality of data obtained from BMS-986158 monotherapy in Parts 1 and 2.

Nivolumab (Part 2)

Nivolumab infusions should start approximately 30 minutes following BMS-986158 administration. Nivolumab should be infused over 30 minutes in adults and adolescents. Further details regarding preparation and administration will be provided separately in site pharmacy training materials.

Guidelines for Nivolumab-related Infusion Reactions

For Grade 1 symptoms: (Mild reaction; infusion interruption not indicated; intervention not indicated)

Remain at bedside and monitor subject until recovery from symptoms. The following prophylactic premedications are recommended for future infusions: diphenhydramine 50 mg (or equivalent) and/or acetaminophen/paracetamol 325 to 1000 mg at least 30 minutes before additional nivolumab administrations.

For Grade 2 symptoms: (Moderate reaction requires therapy or infusion interruption but responds promptly to symptomatic treatment [eg, antihistamines, non-steroidal anti-inflammatory drugs, narcotics, corticosteroids, bronchodilators, IV fluids]; prophylactic medications indicated for \leq 24 hours):

• Stop the nivolumab infusion, begin an IV infusion of normal saline, and treat the subject with diphenhydramine 50 mg IV (or equivalent) and/or acetaminophen/paracetamol 325 to 1000

mg; remain at bedside and monitor subject until resolution of symptoms. Corticosteroid and/or bronchodilator therapy may also be administered as appropriate. If the infusion is interrupted, then restart the infusion at 50% of the original infusion rate when symptoms resolve; if no further complications ensure after 30 minutes, the rate may be increased to 100% of the original infusion rate. Monitor subject closely. If symptoms recur then no further nivolumab will be administered at that visit.

• For future infusions, the following prophylactic premedications are recommended: diphenhydramine 50 mg IV (or equivalent) and/or acetaminophen/paracetamol 325 to 1,000 mg should be administered at least 30 minutes before nivolumab infusions. If necessary, corticosteroids (up to 25 mg of hydrocortisone or equivalent) may be used.

For Grade 3 or Grade 4 symptoms: (Severe reaction, Grade 3: prolonged [ie, not rapidly responsive to symptomatic medication and/or brief interruption of infusion]; recurrence of symptoms following initial improvement; hospitalization indicated for other clinical sequelae [eg, renal impairment, pulmonary infiltrates]. Grade 4: life-threatening; pressor or ventilator support indicated):

• Immediately discontinue infusion of nivolumab. Begin an IV infusion of normal saline and treat the subject as follows: Recommend bronchodilators, epinephrine 0.2 to 1 mg of a 1:1000 solution for subcutaneous administration or 0.1 to 0.25 mg of a 1:10,000 solution injected slowly for IV administration, and/or diphenhydramine 50 mg IV with methylprednisolone 100 mg IV (or equivalent), as needed. Subject should be monitored until the investigator is comfortable that the symptoms will not recur. Nivolumab will be permanently discontinued. Investigators should follow their institutional guidelines for the treatment of anaphylaxis. Remain at bedside and monitor subject until recovery from symptoms.

In the case of late-occurring hypersensitivity symptoms (eg, appearance of a localized or generalized pruritus within 1 week after treatment), symptomatic treatment may be given (eg, oral antihistamine or corticosteroids).

4.2 Non-investigational Product

Other medications used as support or escape medication for preventative, diagnostic, or therapeutic reasons, as components of the SOC for a given diagnosis, may be considered as non-IPs.

4.3 Storage and Dispensing

The product storage manager should ensure that the study drugs are stored in accordance with the environmental conditions (temperature, light, and humidity) as determined by BMS. If concerns regarding the quality or appearance of the study drugs arise, the study drugs should not be dispensed and BMS should be contacted immediately.

Study drug not supplied by BMS will be stored in accordance with the package insert.

IP documentation (whether supplied by BMS or not) must be maintained that includes all processes required to ensure drug is accurately administered. This includes documentation of drug storage,

administration and, as applicable, storage temperatures, reconstitution, and use of required processes (eg, required diluents, administration sets).

4.4 Method of Assigning Subject Identification

This is an open-label study. Enrolled subjects, including those not dosed, will be assigned sequential subject numbers starting with 00001, eg, 00001, 00002, 00003.... 00010. Those enrolled subjects meeting eligibility criteria will be eligible to be dosed. Sequential numbering may restart at 00001 for each participating site as the distinct subject identification number (PID) will ultimately be comprised of the site number and subject number, eg, 0002 00001.

During Part 1, once informed consent has been obtained, the investigator (or designee) will register the subject by transmitting a copy of the completed enrollment worksheet (registration form) to the Sponsor.

The following information is required for registration:

- Subject's date of birth (month and year only are acceptable if required by local regulation)
- Gender
- Diagnosis
- Statement that subject is eligible
- Date of informed consent
- Planned date of first dose

Treatment groups and/or dose levels will be provided to the site study team after the subject has registered and eligibility for the study confirmed. Site personnel/investigator will receive a receipt confirming treatment assignment. A copy of this documentation should remain in the subject's chart.

In the dose escalation phase, if a subject discontinues treatment with BMS-986158 during the DLT Evaluation period for reasons other than DLT, the subject may be replaced if necessary for safety assessments. Replacement subjects will receive the same treatment but will be assigned a new subject number.

Subjects may be permitted to rescreen for the study following agreement between the Sponsor/Medical Monitor and investigators.

In Part 2, during the screening visit, the investigative site will call into the enrollment option of the interactive response technology (IRT) designated by BMS. Enrolled participants, including those not dosed, will be assigned sequential participant numbers for their site starting with 00001, (eg, 00001, 00002, 00003.... 00010). The patient identification number (PID) will ultimately be comprised of the site number and participant number. Once it is determined that the participant meets the eligibility criteria following the screening visit, the investigative site will call the IRT to centrally assign the participant into the appropriate monotherapy or combination therapy cohort. If both monotherapy and combination cohorts are open for a tumor type, the assignment of subjects will alternate between the 2 regimens.

4.5 Selection and Timing of Dose for Each Subject

In each dose escalation part (Part 1) of the study, subjects will be assigned to a specific dose level (see Section 3.1.1). Subjects in the expansion cohorts (Part 2) will be enrolled at or below the MTD or alternative dose as agreed upon by the Sponsor/Medical Monitor and investigators (Section 3.1.2).

4.5.1 Dose Limiting Toxicities

For the purpose of guiding dose escalation, DLTs will be defined based on incidence, intensity, and duration of AEs for which no clear alternative cause is identified. The DLT evaluation period for dose escalation in Part 1 Schedule A is 32 to 35 days (depending on the exact day of the start of Cycle 2); for Schedules B and C it is 35 days. For Part 1 Schedule A, subjects must receive at least 16 of 21 doses of BMS-986158; for Schedule B at least 17 of the 22 doses; and for Schedule C at least 12 of 15 doses to be considered DLT evaluable for dose escalation decisions. The DLT period for safety assessment of BMS-986158 and, if pursued, nivolumab combination therapy in Part 2 will be 28 days for all schedules which excludes a 7-day period for a single dose as in Cycle 1 in Part 1, to allow similar drug exposure and appropriate comparison of the safety profile between Part 1 and Part 2. For Part 2 safety assessment of the combination therapy (if pursued), subjects must receive at least 15 of 20 doses on Schedule A. If alternate schedules are explored, subjects must receive 16 of 21 doses on Schedule B, and 11 of 14 doses on Schedule C. AEs will be graded according to the NCI CTCAE v4.03. For the purpose of subject management, any AE that meets DLT criteria, regardless of the cycle in which it occurs, will lead to dose interruption. Subjects who withdraw from the study during the DLT evaluation interval for reasons other than a DLT may be replaced at the same dose level. The incidence of DLT(s) during the first cycles of treatment (the DLT evaluation period) will be used in dose escalation decisions and to define the MTD. AEs occurring after the DLT period will be considered for the purposes of defining the recommended Phase 2 dose, upon agreement between the Sponsor/ Medical Monitor and investigators, if the AEs are determined to have no clear alternative cause and are not related to disease progression.

DLT(s) will be defined as any of the following events unless a clear alternative cause is identified:

Non-Hematologic DLT:

Any of the following events will be considered a Non-Hematologic DLT:

- \geq Grade 3 Non-Hematologic toxicity, with the following exceptions.
 - ◆ ≥ Grade 3 electrolyte abnormalities that are not complicated by associated clinical AEs, are not clinically significant, last < 72 hours and either resolve spontaneously or respond to conventional medical intervention
 - \geq Grade 3 elevations in serum transaminases (AST, ALT), total bilirubin, alkaline phosphatase that last < 5 days and are not associated with clinical symptoms.
 - Isolated Grade 3 elevation of amylase or lipase not associated with clinical or radiographic evidence of pancreatitis

- Grade 3 nausea, vomiting or diarrhea that lasts < 48 hours and either resolves spontaneously or responds to conventional medical intervention
- Isolated Grade 3 fever not associated with hemodynamic compromise (ie hypotension, clinical or laboratory evidence of impaired end-organ perfusion)
- Grade 3 endocrinopathy that is well controlled by hormone replacement
- Grade 3 fatigue

Alopecia of any grade is not considered a DLT

Hematologic DLT:

- Grade 4 neutropenia \geq 5 days in duration
- Grade 3 febrile neutropenia that lasts > 48 hours
- Grade 4 thrombocytopenia or Grade 3 thrombocytopenia associated with clinically significant bleeding

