3.5 Discontinuation of Subjects following any Treatment with Study Drug

Subjects MUST discontinue BMS-986158 if receiving monotherapy and both BMS-986158 and nivolumab if receiving combination therapy (and non-IP at the discretion of the investigator) for any of the following reasons:

- Subject's request to stop study treatment and/or participation in the study
- Any clinical AE, laboratory abnormality or intercurrent illness which, in the opinion of the investigator, indicates that continued participation in the study is not in the best interest of the subject
- Termination of the study by BMS
- Loss of ability to freely provide consent through imprisonment or involuntarily incarceration for treatment of either a psychiatric or physical (eg, infectious disease) illness
- Inability to comply with protocol

- Discretion of the investigator
- AEs requiring discontinuation as outlined in the Dose Modification section (See Section 4.5.2)
- Pregnancy
- Documented and confirmed PD as defined by RECIST v1.1 (for solid tumors, see Appendix 04), or Lugano 2014 (for hematoligic tumors see Appendix 09), or PCWG3 (for CRPC and NEPC see Appendix 12) unless participant meets criteria for treatment beyond progression (Section 3.6)

All subjects who discontinue investigational product (IP) should comply with protocol specified follow-up procedures as outlined in Section 5. The only exception to this requirement is when a subject withdraws consent for all study procedures including post-treatment study follow-up or loses the ability to consent freely (ie, is imprisoned or involuntarily incarcerated for the treatment of either a psychiatric or physical illness).

If study drug is discontinued prior to the subject's completion of the study, the reason for the discontinuation must be documented in the subject's medical records and entered on the appropriate CRF page.

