4.5.2 Guidelines for Dose Modifications

Subjects will be monitored continuously for AEs while on study therapy. Subjects will be instructed to notify their physician immediately for any and all AEs. The criteria presented in this section and Table 4.5.2-1 for dose modifications and delays for BMS-986158 are meant as general guidelines.

- Subjects will continue to receive therapy as long as they have not had disease progression or an AE requiring dose modification, as described below.
- Dose modifications, interruptions, or delays may occur in the setting of lower grade AEs and/or be more conservative than indicated in Table 4.5.2-1 based on the clinical judgment of the investigator, and in consultation with the Sponsor/Medical Monitor.
- For BMS-986158, dose reductions should be to the previous lower dose level, or to a dose level in between the previous dose level and the current dose level, after discussion between Sponsor/Medical Monitor. A decision to remain at the current dose level requires a discussion and an agreement between the investigator and the Sponsor/Medical Monitor.
- If several AEs of varying grade or severity occur simultaneously, the dose modification applied should be the greatest reduction applicable based on the worse grade (or severity) observed among the AEs reported.
- Assessment of causality (chronology, confounding factors such as disease, concomitant medications, diagnostic tests and previous experience with the agent) must be determined and documented by the investigator, prior to dose modification.
- If the same Grade 3 non-hematologic AE recurs despite a dose reduction, a second dose reduction versus discontinuation of the subject from further protocol therapy will be discussed and agreed upon by the Sponsor/Medical Monitor and investigators.
- Subjects who experience a Grade 4 non-hematologic AE will not receive additional protocolrelated therapy and will be removed from study unless discussed and agreed upon by the

Sponsor/Medical Monitor and investigators that it is in the best interest of the subject to receive additional therapy with BMS-986158 (for example, if the subject has demonstrated a response to therapy).

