- No more than 2 dose level reductions of BMS-986158 will be allowed per subject. If a third dose reduction is required, the subject must discontinue BMS-986158 (and nivolumab, if receiving combination therapy based on response to therapy). Dose re-escalation after a dose reduction may occur in limited circumstances (such as a change in attribution of an AE, or if re-escalation is in the best interest of the subject) after discussion and agreement of the Sponsor/Medical Monitor and investigators. The number of dose modifications needed for a subject should be discussed and agreed between the investigator and the Sponsor/Medical Monitor.
- Skipped doses will not be administered within the same cycle.
- For an AE requiring dose modification, BMS-986158 (and nivolumab for subjects receiving combination therapy) should be interrupted to allow recovery from the AE. Re-initiation of study drug cannot occur until AE decreases to ≤ Grade 1 or baseline assessment. In case of delayed recovery to ≤ Grade 1 or baseline (except for alopecia) from treatment-related AEs that results in a delay of treatment for > 30 days, the subject will not receive additional protocol-related therapy and will be removed from study unless discussed and agreed upon by the Sponsor/Medical Monitor and investigators that it is in the best interest of the subject to receive additional therapy with BMS-986158 (for example, if the subject has demonstrated a response to therapy).
- For patients receiving combination therapy, if 1 study drug must be discontinued, the other study drug may be continued as single agent therapy based on discussion with Sponsor/Medical Monitor and the investigator.
- For subjects in Part 2 monotherapy expansion or (if pursued) combination expansion who report an AE requiring dose modification, the dose of BMS-986158 should be reduced from 3.75 mg to 3 mg. See Table 4.5.2-1.

For data collection and analysis purposes, all subjects will continue to be classified by the original treatment arm.

Table 4.5.2-1:DoseEven	Modification Criteria for BMS-986158 Drug-Related Adverse			
Adverse Event	Initial Action	Dose Modification		
Grade 4 febrile neutropenia	Discontinue BMS-986158	Discontinue BMS-986158		
Grade 3 febrile neutropenia	Hold BMS-986158 until return to baseline or Grade 1	1st event: Consider reduction by 1 dose level. 2nd event: Reduce by 1 dose level		

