≥ Grade 4 hematologic toxicity (neutropenia or thrombocytopenia)	Hold BMS-986158 until returns to baseline or Grade 1.	1st event: Consider reduction by1 dose level.2nd event: Reduce by 1 dose level.		
Grade 3 thrombocytopenia with clinically significant bleeding	Hold BMS-986158 until return to baseline or Grade 1	1st event: Consider reduction by 1 dose level. 2nd event: Reduce by 1 dose level		
≥ Grade 3 non-hematologic AE in subjects receiving maximum medical management.	Hold BMS-986158 until resolves to baseline or Grade 1.	1st event: Consider reduction by 1 dose level.2nd event: Reduce by 1 dose level.		
QTcF > 500 msec confirmed by at least one repeat ECG	Discontinue BMS-986158	Discontinue BMS-986158		
≥ Grade 3 diarrhea not adequately controlled with medication at maximum doses	Hold BMS-986158 until resolves to baseline or Grade 1.	1st event: Consider reduction by 1 dose level.2nd event: Reduce by 1 dose level.		

T 11 4501 . . • . . .

If needed, based on the occurrence of DLTs or other AEs, an individual subject enrolled on any arm may have the BMS-986158 schedule revised to match the alternate schedule on an another arm, at the agreement of the investigator and Sponsor/Medical Monitor, in order to better manage the overall tolerability of study treatment. This schedule change may be in lieu of dose modification shown in Table 4.5.2-1. At the agreement of the investigator and Sponsor/Medical Monitor, subjects who have already had dose reduction may be restarted at the original dose under the revised schedule. For data collection and analysis purposes, all subjects will continue to be classified by the original treatment arm.

Reasons for dose modifications or delays, the supportive measures taken and the outcome must be documented in the subject's chart and recorded in the CRF.

Subjects will be monitored continuously for AEs while on study therapy. Subjects will be instructed to notify their physician immediately for any and all toxicity. The criteria presented in this section for dose modifications and delays are meant as general guidelines.

Assessment of causality (chronology, confounding factors such as disease, concomitant medications, diagnostic tests and previous experience with the agent) must be determined and documented by the investigator, prior to modifying any drugs.

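### Grade 4 febrile neutropenia requires treatment to stop but is missing from the hematologic DLT list, so an episode that meets no other criterion is not counted as a DLT

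*Protocol*

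**What the plan says.** Protocol Section 4.5.1 defines a DLT as any event on its list unless a clear alternative cause is identified. The hematologic part has three bullets: Grade 4 neutropenia of at least 5 days; "Grade 3 febrile neutropenia that lasts > 48 hours"; and Grade 4 thrombocytopenia, or Grade 3 with clinically significant bleeding. The general rule for severe events, at or above "Grade 3 Non-Hematologic toxicity, with the following exceptions", covers non-hematologic toxicity only.

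Table 4.5.2-1 (Section 4.5.2) has a separate row for "Grade 4 febrile neutropenia", and both action columns say to discontinue BMS-986158. Section 4.5.2 says its criteria "for dose modifications and delays for BMS-986158 are meant as general guidelines". Section 3.5, however, lists "AEs requiring discontinuation as outlined in the Dose Modification section (See Section 4.5.2") among the reasons for which a subject must stop.

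Section 3.1.1 requires 16 of 21, 17 of 22 or 12 of 15 doses (Schedules A, B, C) for a subject to be DLT-evaluable. Only a subject with a DLT is evaluable regardless of doses. Under Sections 4.4 and 4.5.1, a subject who stops for a reason other than a DLT may be replaced. SAP Section 2.1 repeats the evaluability rule, SAP Section 7.6.9 lists the available DLT data, and neither widens the definition.

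**The concern.** Assessing DLTs and the MTD is part of the primary objective, and Section 4.5.1 holds the only DLT list. Of the four hematologic rows in Table 4.5.2-1, the one row that requires discontinuation is the one with no corresponding DLT bullet. Read literally, the less severe grade can count towards the mTPI decision while the grade that ends treatment does not. The event can drop out of the count in two ways. An early event leaves the subject unevaluable and replaceable. A later one makes the subject an evaluable non-DLT. Either way, the mTPI table is entered with one DLT fewer than a clinician would expect.

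**Working it through.** **1. Hematologic rows of Table 4.5.2-1 against the DLT bullets.**

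| Row in Table 4.5.2-1 | Action | Bullet in Section 4.5.1 |
|---|---|---|
| "Grade 4 febrile neutropenia" | Discontinue | None |
| Grade 3 febrile neutropenia | Hold; consider reduction, reduce on second event | Yes, if > 48 hours |
| "≥ Grade 4 hematologic toxicity (neutropenia or thrombocytopenia") | Hold; same | Yes (neutropenia if >= 5 days) |
| "Grade 3 thrombocytopenia with clinically significant bleeding" | Hold; same | Yes |

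**2. Which episodes remain uncovered.** Grade 4 febrile neutropenia is still a DLT if the Grade 4 neutropenia lasts 5 days or more, if a Grade 3 phase lasts more than 48 hours, or if a qualifying >= Grade 3 non-hematologic event occurs with it. On the last route, "Isolated Grade 3 fever not associated with hemodynamic compromise" is excepted, so fever with such compromise would qualify. The gap is what is left, for example a shorter episode with none of these.

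**3. What happens to that subject.** With a 7-day Cycle 1, the minimum dose count is reached on these study days:
- Schedule A: dose 1 on day 1, doses 2-6 on days 8-12, 7-11 on days 15-19, 12-16 on days 22-26. Dose 16 is on day 26.
- Schedule B: doses 2-15 on days 8-21, with the next cycle from day 29. Dose 17 is on day 30.
- Schedule C: doses 2-8 on days 8-14, with the next cycle from day 29. Dose 12 is on day 32.

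A stop before that dose leaves the subject unevaluable; a stop after it leaves an evaluable non-DLT.

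**4. Reproducing the decision rule.** Appendix 1 uses a target of 27% and an equivalence interval of 25% to 29%. Unit probability mass is the posterior probability of each interval divided by its length (0.25, 0.04, 0.71). I assume a Beta(1,1) prior and a DU rule of P(rate > 27%) > 95%; with these, all 135 cells of Appendix 1 are reproduced.

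| DLTs/evaluable | Below 25% | 25-29% | Above 29% | Decision |
|---|---|---|---|---|
| 0/3 | 2.73 | 1.56 | 0.36 | Escalate |
| 0/4 | 3.05 | 1.42 | 0.25 | Escalate |
| 1/4 | 1.47 | 2.10 | 0.77 | Stay |

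Take a cohort of four with one such event. Counted as a DLT it is 1/4, Stay. As an evaluable non-DLT it is 0/4, Escalate. If the subject is unevaluable it is 0/3, Escalate.

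**5. Posterior risk.** Table 8.1-1 uses Beta(1 + x, 2.7 + n - x). For P(DLT rate > 33%) this formula gives 16.2% at 1/6 and 41.1% at 2/6 (printed 16% and 41%). At the cells above it gives 10.2% (0/3), 6.8% (0/4) and 29.4% (1/4).

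**6. Combination phase, if pursued.** Table 3.1.2.2-1 gives Expand at 1/6 and Stay at 2/6. With Beta(1 + x, 2 + n - x), P(DLT rate > 33%) is 20.1% and 47.6%; Table 3.1.2.2-2 prints 20% and 47%.

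**7. How often.** Protocol Section 1.4.4 (cutoff 21-Dec-2018, 81 treated) names no febrile neutropenia among related Grade 3-4 events, and Section 1.5 names none among the unexpected serious events. Taking that as 0/81, the exact two-sided 95% upper bound is 1 - 0.025^(1/81) = 4.45%. This bounds any related febrile neutropenia of Grade 3-4; the uncovered episodes in step 2 are a subset.

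**The case against.** The case for leaving the text alone is reasonable:

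- Any >= Grade 2 toxicity without an alternate cause (fatigue and alopecia excepted) ends the 100% dose steps (Section 3.1.1), so a later Escalate moves by a smaller increment.
- Replacement is discretionary. In Section 3.1.1 it is for subjects with insufficient safety data and needs agreement of the sponsor and investigators.
- In Part 2, enrollment may be interrupted when drug-related AEs requiring dose modification exceed 29% in a tumor cohort (Section 3.1.2.1), or when drug-related toxicity requiring discontinuation exceeds 33% at a dose level (Section 3.1.2.4).
- AEs by worst grade and AEs leading to discontinuation are primary endpoints and are tabulated (SAP Sections 7.6.3 and 7.6.5).
- 81 of about 90 Part 1 subjects had been treated and the Part 2 dose was already chosen. Adolescent monitoring has no decision table, and the combination phase is conditional and outside the SAP's scope.
- Table 4.5.2-1 need not mirror the DLT list: Grade 4 neutropenia of any duration is held, but only 5 days or more is a DLT.

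All of this stands, and it limits the consequences. None of it puts the event into the DLT count. The general-guidelines wording does not help either, because Section 3.5 makes the stop mandatory.

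A reader might infer that the DLT rate or the chosen dose is biased downward. The documents do not support that: they report no such event and no subject dropped for this reason. The 1 of 81 subjects with related Grade 3-4 neutropenia is not a substitute rate, since it is neither febrile nor limited to the DLT window.

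**Conclusion.** The gap is real and narrow. By its literal terms, Section 4.5.1 does not count a Grade 4 febrile neutropenia that meets no other DLT criterion, although the protocol requires treatment to end. In a cohort of four, one such event turns Stay at 1/4 into Escalate at 0/3 or 0/4. Among six combination subjects, it turns Stay at 2/6 into Expand at 1/6.

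The expected effect is small: 0/81 reported, upper bound about 4.5% for any related Grade 3-4 febrile neutropenia, and less for the uncovered episodes. This assumes that the Section 1.4.4 list of related Grade 3-4 events is complete for febrile neutropenia. The list is preliminary and is introduced as what the events include. The wording matters for any remaining Part 1 subjects, the first 3 to 4 adolescents monitored for DLT, and the combination phase if pursued, which has its own minimum of 15 of 20 doses and its own replacement rule.

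The point should not be read as a challenge to the sponsor's exceptions for Grade 3 fatigue, Grade 4 neutropenia under 5 days, or Grade 3 febrile neutropenia of 48 hours or less. Those are stated choices. Severity: minor.

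**What to change.** In Section 4.5.1, replace the febrile neutropenia bullet with: *Grade 4 febrile neutropenia of any duration, or Grade 3 febrile neutropenia lasting > 48 hours.*

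The cost is one reworded bullet, with no change to the mTPI tables, the sample size or the data collected. The stated exceptions stay as they are. No SAP change is needed. In particular, a sensitivity MTD that counts every drug-related unevaluable subject as a DLT is not recommended, because it would also count events that the sponsor chose to exempt.
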